9. STATISTICAL ANALYSIS

9.1 Primary study parameter(s)

The primary outcome is the proportion at risk of HCV infection (as determined by a HCV-MOSAIC score ≥ 2.0) during the run-in versus intervention periods. The score is calculated by summing up the beta-coefficients specific to six self-reported risk factors when present in the previous 6 months (see [Chapter 7.1.1](#)). The HCV-MOSAIC risk score has been previously validated for acute (primary) HCV-infection in HIV-positive MSM and the optimal cut-off to predict HCV positivity was defined at ≥ 2.0 .(65) In addition, we recently evaluated whether the risk score could also identify individuals at high-risk of HCV reinfection, showing comparable performance (The Area Under the ROC Curve = 0.76) to that of primary acute HCV-infection.(66)

The six items of the HCV-MOSAIC risk score will be obtained using the answers from the study questionnaire every six months. The proportion achieving the primary outcome will be summarized at month 6, 12, 18 and 24 visits within each study arm. The probability of the primary outcome will be compared between the run-in (month 6) and intervention periods (month 12, month 18, month 24) using a mixed-effect logistic regression model. In this model, each individual will serve as their own control and between-individual differences at baseline will be accounted for using a random-intercept. Pre versus post-intervention odds ratios (ORs) and their 95% confidence intervals (CI) will be estimated and stratified on study arm, allowing us to identify interventions with significant differences. No multivariable adjustments will be applied. Additional analysis will be conducted in which ORs between arms will be compared by including and testing an interaction term between period and arm in the model (two arms at a time, for a possible three comparisons). No *p*-value adjustments will be made for multiple comparisons to avoid unnecessary correction on the possibly underpowered test for interaction.(67)

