2.2.2. Comparative analysis

The primary endpoint is compared between the run-in period (i.e., at M0, M6) and at each time point during the intervention period (i.e., at M12, M18, M24) using a mixed-effect logistic regression model. In this model, each individual serves as their own control and between-individual differences at baseline are accounted for using a random-intercept. Odd ratios (OR) comparing the odds of run-in versus intervention time points, along with their 95% confidence intervals (CI), are estimated and stratified on study arm. These stratified analysis are performed by including an interaction term between arm and study time point (along with their individual covariate) in the model, while study time points are statistically tested within strata of the study arms. Comparisons between run-in and intervention time points are systematically conducted as follows:

- Unadjusted;
- Adjusted on the randomisation strata (country and, if sufficient numbers of individuals in each intervention arm are available, inclusion centre [3]);
- Adjusted on covariates that could potentially affect the evaluation of the primary outcome

Incidence rates of HCV reinfections and STIs are calculated during the run-in and interventions periods, separately. Considering that few HCV reinfections are likely to occur,

we intend to analyse the relative difference in incidence rates between periods using a Bayesian exponential survival regression model with non to weakly informative *a priori* distributions [4, 5]. The relative difference in incidence rates of STIs are compared between periods using a Poisson regression model with ln of person years of observation as an offset. These models are run on both the overall study population and stratified by treatment arm (using the same model configuration of fixed-effect covariates as in the primary endpoint).

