Changes are described for HCV related risk behaviour and sexual wellbeing (see paragraphs 3.5.3 and 3.5.4) during run-in (i.e., M0 and M6) versus intervention period (i.e., M12, M18, M24). We use logistic (for binary outcomes) and linear (for continuous outcomes) regression models, corrected for repeated measurements within individuals using a random-intercept for participant. The relative changes in each endpoint are compared between run-in and intervention periods. These models are run on both the overall study population and stratified by treatment arm (using the same model configuration of fixed-effect covariates as in the primary endpoint).

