3.4. PRIMARY ENDPOINT

3.4.1. Main analysis

- **Definition**

The proportion of participants achieving an HCV-MOSAIC risk score ≥ 2.0 compared between the run-in (i.e., M0 to M6) and intervention periods (i.e., M12 to M24). ORs are calculated along with their 95%CI in the ITT and PP population as described in paragraph 2.1.1.

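### The mixed models allow for repeated measures only through a random intercept; if answers grow less alike over time, the pooled and late-visit intervals are too narrow, and robust standard errors would cheaply prevent this

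*SAP*

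**What the plan says.** SAP 2.2.2 compares the run-in with the intervention period "at each time point during the intervention period (i.e., at M12, M18, M24) using a mixed-effect logistic regression model". The fixed effects are arm, time point and their product ("including an interaction term between arm and study time point"), and time points are tested within arm. The only allowance for repeated answers is this: "In this model, each individual serves as their own control and between-individual differences at baseline are accounted for using a random-intercept". The same section treats the secondary behaviour and wellbeing models alike: they are "corrected for repeated measurements within individuals using a random-intercept for participant".

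Protocol 9.1 has the same structure: "between-individual differences at baseline will be accounted for using a random-intercept".

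Three contrasts can be read from the documents, and the size of the problem differs between them:

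- SAP 2.2.2: run-in (M0 and M6) against each of M12, M18 and M24.
- SAP 3.4.1: period against period, "compared between the run-in (i.e., M0 to M6) and intervention periods (i.e., M12 to M24".
- Protocol 9.1: month 6 alone as run-in, "compared between the run-in (month 6) and intervention periods (month 12, month 18, month 24) using a mixed-effect logistic regression model".

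Neither document names a robust variance, a serial correlation term or a random period effect. The sensitivity analyses in SAP 2.1.1 concern use of the intervention, risk status at randomisation, and adherence and loss to follow-up. None varies the correlation structure or the variance estimator.

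**The concern.** On the latent scale, a random intercept treats answers given 24 months apart as no less alike than answers given 6 months apart. It also lets every man in an arm change by the same amount. If either assumption fails, contrasts that set early visits against late ones carry variance that the model does not count.

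The documents give some reason to expect individual drift. Protocol 1.5 describes varied reactions to a negative test, Protocol 5.1 builds the behavioural intervention around goals each man chooses, and SAP 3.3.3 plans to describe how COVID-19 measures and mpox affected behaviour.

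The stake is the trial's main inference. There is no untreated arm, and Protocol section 3 sets the aim as finding a significant fall within each arm. An interval that is too narrow makes an arm with no true change look effective more often than the stated 5%.

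**Working it through.** **Inputs from the documents.** 78 men per arm, 60% at risk in the run-in, type I error 0.05, a 22-point absolute reduction (SAP 1.4); five questionnaires six months apart (SAP 1.2.1). Two-sided tests are assumed, in line with the 95% intervals.

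**The plan's own figure.** For two independent proportions, n = [1.96·√(2·0.49·0.51) + 0.842·√(0.60·0.40 + 0.38·0.62)]² / 0.22² ≈ 80 per group, and power at 78 is 0.791. The stated 80% is reproduced. This calculation uses no within-person correlation, so it gives no guide to that quantity.

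**Assumption.** The between-visit correlation is not in the documents, so it is varied below.

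**Hand check on a linear scale.** Let r1 to r4 be the correlations of at-risk status 6, 12, 18 and 24 months apart. The variances, in units of the single-visit variance, are:

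- Pooled period: 5/6 + r1/2 + (4r1 + 2r2)/9 − (r1 + 2r2 + 2r3 + r4)/3
- M12 v run-in: 1.5 − r1/2 − r2
- M18 v run-in: 1.5 + r1/2 − r2 − r3
- M24 v run-in: 1.5 + r1/2 − r3 − r4

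A random-intercept model in effect uses one average correlation r̄, which gives (5/6)(1 − r̄) for the pooled contrast and 1.5(1 − r̄) for each single visit.

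Take latent serial correlation 0.8, for which r1–r4 = 0.59, 0.44, 0.34, 0.27. Then r̄ = (4·0.59 + 3·0.44 + 2·0.34 + 0.27)/10 = 0.463.

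- Pooled: true 0.8333 + 0.295 + 0.36 − 0.8067 = 0.6817; model (5/6)(0.537) = 0.4475. SE ratio √(0.4475/0.6817) = 0.81, so the error rate is 2Φ(−1.96·0.81) = 11.2%.
- M12: true 0.765, model 0.8055. Ratio 1.03, error 4.4%.
- M18: true 1.015, model 0.8055. Ratio 0.89, error 8.1%.
- M24: true 1.185, model 0.8055. Ratio 0.82, error 10.6%.

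Individual drift can be checked the same way, with correlation 0.54 within a period and 0.41 across periods, so r̄ = 0.462. Pooled: true 0.8333 + 0.27 + 0.36 − 0.82 = 0.6433, model 0.4483, error 10.2%. M12: true 0.95, model 0.807, error 7.1%.

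**Simulation of the logistic model.** The first three rows below use three arms of 78, five visits, 60% at risk throughout, a random-intercept logistic model with arm by time fitted by maximum likelihood, and 1500 trials (4500 arm-level tests) per pattern. The drift row uses one arm of 78 and 1500 replicates. Entries are rejection rates (%) with model-based standard errors.

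| Assumed pattern (latent correlation) | Pooled period | M12 | M18 | M24 | Protocol, M6 only |
|---|---|---|---|---|---|
| Equal, 0.70 | 5.1 | 4.4 | 4.9 | 4.9 | 4.7 |
| Partial fading: 0.70–0.78 at 6 months to 0.46–0.62 at 24 | 7.4–8.6 | 4.4–4.8 | 6.3–7.1 | 6.9–8.5 | 5.3–5.9 |
| Pure serial decay: 0.6, 0.8 or 0.9 per 6 months | 10.2–12.0 | 4.2–4.5 | 7.8–8.8 | 9.6–11.8 | 6.3–6.8 |
| Drift: 0.75–0.80 within period, 0.50–0.60 across | 9.2–13.3 | 6.7–8.2 | 5.9–7.9 | 7.4–9.3 | 6.9–8.9 |

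Under pure decay the pooled standard error is 17–21% too small (for example 0.346 against an empirical 0.440). Under partial fading it is 10–13% too small (for example 0.277 against 0.318). A separate run of 600 replicates gave a pooled rate of 3.8% with equal correlation and 8.7–11.3% with fading or drift.

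**With robust standard errors on the same model.** Single-contrast rates are 4.8–6.0% in the first three patterns, 4.0–5.7% under drift, and 4.3–6.5% for the pooled contrast in the separate run.

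**Power at 60% to 38% (200 trials each).** For the pooled contrast, robust 99.2% against model-based 99.8% (serial decay 0.8), and 99.7% against 99.8% (partial fading). For M24, 93.8% against 97.5%, and 96.0% against 97.8%.

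**The case against.** A random intercept is a conventional and openly stated choice, and this is a pilot (Protocol section 3), labelled phase 2 in the SAP. At the planned effect the pooled conclusion would be the same with either standard error. These points stand, and they keep the matter below must-fix.

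A reader might infer that every within-arm interval is too narrow and that the error rate doubles throughout. The documents do not support that. They give no between-visit correlation from which to claim it. SAP 2.2.2 tests each visit, and under fading alone the M12 interval is not too narrow. The protocol's month-6-only contrast stays at 5.3–6.8% under fading. Doubling needs pure serial decay or marked individual drift; a stable personal tendency plus some decay gives about 1.4–1.7 times nominal for the pooled and M24 contrasts.

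A reader might also put the chance of at least one false-positive arm at about a third, since 1 − (1 − 0.12)³ = 0.32 against 1 − 0.95³ = 0.14. That rests on a single assumed rate for the most affected contrasts. At 7% the same sum gives 0.20, and the 14% comes from testing three arms without adjustment, which is a separate matter.

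The simulations use complete data. They do not represent the ITT rule in SAP 2.1.1 that counts men lost to follow-up as at risk, nor the linear and Poisson secondary models.

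**Conclusion.** The point holds in conditional form. The plan relies on equal correlation between all visits and has no safeguard if that fails. If correlation fades or men change differently, within-arm type I error for the pooled and M24 contrasts is about 7–12% over plausible assumed patterns (one drift pattern reached 13.3% for the pooled contrast), and about 6–9% for M18. M12 is essentially unaffected by fading alone, though not by drift (6.7–8.2%). With equal correlation there is no problem.

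The rates depend on assumed correlations and apply to the binary endpoint with complete data. The same mechanism applies to the secondary mixed models, but its size there has not been calculated. This is a worthwhile, inexpensive improvement rather than an error that invalidates the analysis.

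**What to change.** Add to SAP 2.2.2 that all intervals and tests from the planned mixed-effect models use robust (sandwich) standard errors clustered on participant, and that the same rule covers the secondary mixed models. A random period effect could be added as a sensitivity check.

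Keep the mixed model. Replacing it with GEE would change the odds ratio from participant-specific to population-averaged. For 60% to 38% the latter is (0.38/0.62)/(0.60/0.40) = 0.41, whereas the simulated participant-specific coefficients of −1.55 and −1.71 correspond to about 0.21 and 0.18. Standard GEE also needs stronger missing-data assumptions, which matters for the per-protocol analysis of available observations.

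Cost: one sentence and one software option. Intervals become somewhat wider where the correlation is unequal. At the planned effect the pooled contrast loses under one point of power, and M24 about 2–4 points.

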1.2. TRIAL DESIGN

1.2.1. Study design and methods

This study is an international, multi-centre, phase 2, 3-arm, randomized trial (RT) comparing run-in and intervention periods to evaluate the effect of an online behavioural intervention, a home-based sampling for testing intervention, or both on self-reported behaviours associated with HCV acquisition. The first 6 months of the trial includes follow-up with no intervention (termed the “run-in” period) during which participants receive standard care. At month (M) 6, participants are randomly assigned, with an allocation ratio of 1:1:1, to one of the following three arms: (1) a targeted, online behavioural intervention; (2) a participant-initiated, home-based HCV-RNA self-sampling test service using dried blood spots (DBS); (3) consists of a combination of intervention I and II. Participants continue the intervention for 18 months (termed the “intervention” period) in addition to standard care. During both the run-in and intervention periods, five online questionnaires measuring risk behaviour over the past 6 months are administered (i.e., at M0, M6, M12, M18 and M24 of the study).

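### In the intention-to-treat analysis the arms could share one run-in level, lowering the variance of each within-arm log odds ratio by about 7–11% per visit at latent correlations of 0.75 to 0.5

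*SAP*

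**What the plan says.** SAP 1.2.1 describes a common run-in: "The first 6 months of the trial includes follow-up with no intervention", with standard care for all. Allocation comes after it: "At month (M) 6, participants are randomly assigned, with an allocation ratio of 1:1:1".

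SAP 2.2.2 states the primary comparison. The endpoint (HCV-MOSAIC score of 2.0 or more) is "compared between the run-in period (i.e., at M0, M6) and at each time point during the intervention period (i.e., at M12, M18, M24". The arm-specific odds ratios come from one mixed-effect logistic model "including an interaction term between arm and study time point (along with their individual covariate) in the model", with time points tested inside each arm, and "between-individual differences at baseline are accounted for using a random-intercept". With arm, time point and their product all in the model, the run-in level is free to differ between arms.

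Three further facts bear on the size of the point:

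- Protocol 9.1 uses a narrower run-in. The outcome "will be compared between the run-in (month 6) and intervention periods (month 12, month 18, month 24) using a mixed-effect logistic regression model".
- SAP 3.4.1 sets M0 to M6 against M12 to M24, which can be read as one pooled intervention period instead of three separate visits.
- Neither document gives a within-person correlation or a random-intercept variance, and neither mentions a common run-in level.

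**The concern.** The run-in answers describe a period in which no one had been offered an intervention, and the arm label is attached at random afterwards. Any run-in difference between arms in the full randomised set is therefore chance. The SAP model estimates three run-in levels, each from about 78 men, when there is one quantity to estimate from about 234. The chance part of each arm's run-in level passes into that arm's change, and into any comparison of changes between arms. The random intercept removes only some of it.

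At stake is precision. The confidence intervals are wider than the same data allow, and the loss is largest for the between-arm comparison of changes. Protocol 9.1 itself regards that interaction test as possibly underpowered, and Protocol 4.4 needs a reduction of 0.43 in one arm against 10% in the other to reach 80% power.

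**Working it through.** **Inputs.** 78 men per arm, three arms, 60% at risk in the run-in, an absolute fall of 22 points to 38%, type 1 error 0.05 (SAP 1.4; two-sided is assumed). M0 and M6 are treated as one reference level, with M12, M18 and M24 separate (SAP 2.2.2). The within-person correlation is an assumption and is varied.

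**1. The plan's own figure.** Two-proportion normal approximation, mean proportion 0.49:

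z = [0.22 × √78 − 1.96 × √(2 × 0.49 × 0.51)] / √(0.60 × 0.40 + 0.38 × 0.62) = (1.943 − 1.386) / 0.690 = 0.81, power 0.79.

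The stated 80% is reproduced to within a point.

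**2. Closed form, linear approximation.** Let every pair of visits have correlation r, with unit variance. Variances below are to be divided by the number of men per arm.

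- Arm-specific levels, one post visit: 1 + (1 + r)/2 − 2r = 1.5(1 − r).
- With a shared level, the arm's deviation from the overall run-in mean (variance (1 + r)/3) enters with weight 2r/(1 + r) instead of 1. The variance falls by [(1 − r)/(1 + r)]² × (1 + r)/3 = (1 − r)²/[3(1 + r)].
- Relative saving, one visit: (2/9)(1 − r)/(1 + r).
- Three post visits pooled: the starting variance is 5(1 − r)/6, so the saving is (2/5)(1 − r)/(1 + r).
- Difference in change between two arms, one visit: (1/3)(1 − r)/(1 + r).

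| r | within arm, one visit | within arm, pooled | between arms, one visit |
|---|---|---|---|
| 0.3 | 12.0% | 21.5% | 18% |
| 0.5 | 7.4% | 13.3% | 11% |
| 0.7 | 3.9% | 7.1% | 6% |

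**3. The SAP's logistic model.** Exact expected information for the random-intercept logistic model, 78 per arm, with arm-specific and with shared run-in levels. For 60% to 38%, one visit:

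| random-intercept variance | latent correlation | correlation of two binary answers | variance saving | power, arm-specific → shared |
|---|---|---|---|---|
| 0.5 | 0.13 | 0.10 | 18.0% | 0.910 → 0.954 |
| 2 | 0.38 | 0.27 | 12.9% | 0.953 → 0.974 |
| 3.29 | 0.50 | 0.35 | 10.9% | 0.970 → 0.983 |
| 8 | 0.71 | 0.52 | 7.9% | 0.991 → 0.994 |
| 12 | 0.78 | 0.59 | 6.9% | 0.995 → 0.997 |

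A small simulation (60 trials) at variance 2 gave 12.5% against the 12.9% computed. For a smaller fall, 60% to 50%, the one-visit saving is 11.1% at latent correlation 0.5 and 7.0% at 0.75, with power moving from 0.44 to 0.48 and from 0.57 to 0.61.

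**4. Other contrasts.** At latent correlations of 0.75 to 0.5, pooling the post visits gives a saving of about 12–20%, and the change compared between two arms gains about 11–17% per visit. If M6 alone is the run-in (Protocol 9.1), the within-arm saving per visit is larger: 14.3% to 29.6% over the variances in the table.

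**5. Interval width.** √(1 − 0.07) = 0.964 and √(1 − 0.11) = 0.943, so a 7–11% variance saving makes intervals about 4–6% narrower. At 18%, √0.82 = 0.906, about 9% narrower.

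**6. If run-in levels are not equal.** Suppose one arm's true run-in level differs by 5 points from the other two. It then lies 5 × 2/3 = 3.33 points from the overall mean, and the bias in its change is 3.33 × (1 − r)/(1 + r): 1.1 points at r = 0.5 and 2.7 points at r = 0.1.

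**The case against.** The strongest reply is that nothing is broken. The arm-specific model is unbiased for its stated contrast, the random intercept already absorbs part of the chance imbalance, and evaluation inside each arm with each man as his own control is a deliberate design choice. Under a shared level, (2/3)(1 − r)/(1 + r) of an arm's run-in reference comes from men in the other arms: 36% at r = 0.3 and 22% at r = 0.5. This stands as a description of the trade. It makes the change a gain in efficiency and not the repair of an error.

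A reader might infer that the change is free because randomisation guarantees the constraint. The documents support that only for men as randomised. SAP 2.1.1 also runs a per-protocol analysis that removes men who did not receive their intervention, and a sensitivity analysis of intervention users. Both sets are formed after allocation, by behaviour that can differ between arms, so step 6 applies to them. In addition, the M6 questionnaire and randomisation fall in the same month, Protocol 7.2 says participants learn their arm immediately, and the order of the two is not stated. SAP 2.3.1 ends run-in follow-up at randomisation, which fits M6 answers coming first but does not say so.

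A reader might also infer that the primary tests are short of power and that this rescues them. At the planned effect they are not: step 3 gives 0.91 or more for a single visit before any change.

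Lastly, the SAP's own between-arm endpoint (2.1.2 and 3.5.5) compares proportions at the end of follow-up, so the between-arm gain computed here applies to the interaction analysis of Protocol 9.1.

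**Conclusion.** The point holds as a cheap improvement to the ITT analysis. Among men as randomised, one run-in level is correct by design, and SAP 2.2.2 does not use it. With the SAP's coding the saving in variance is about 7–11% per visit at latent correlations of 0.75 to 0.5, and up to about 18% at low correlation. It is about 12–20% at the same 0.75 to 0.5 if SAP 3.4.1 means a pooled intervention period. Quoting the pooled figure for every within-arm estimate would overstate the gain for the visit-by-visit contrasts that SAP 2.2.2 specifies.

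These figures rest on an assumed correlation, a random-intercept structure and complete data. The price is that the three within-arm estimates become correlated and each borrows run-in data from the other arms. The comparison remains before against after: a shared run-in level does not supply the concurrent control that the design lacks.

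**What to change.** In SAP 2.2.2:

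1. For ITT, drop the arm main effect and keep visit and arm-by-post-randomisation-visit terms, so that all arms share one run-in level. Report the arm-specific model beside it as a check.
2. Keep arm-specific run-in levels for the per-protocol and intervention-user sets. Do the same for any analysis from which men who never received an intervention have been removed, an exclusion that SAP 2.1 leaves open for discussion.
3. Count M6 answers as run-in only if they were given before allocation was revealed, and state this.
4. State whether the run-in is M0 and M6 or M6 alone, and whether post visits are separate or pooled, since the gain depends on both.
5. Note that the three within-arm estimates are correlated.

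The cost is a few lines of specification and one extra model fit, with no new data. The change should be made before the analysts, who stay blinded under SAP 2.1, learn the allocation.

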9.2 Secondary study parameter(s)

Incidence rates of HCV reinfections and STIs will be calculated at the end of follow-up. Incidence of HCV reinfection will be examined during the lead-in and intervention periods of the RT. Considering few HCV reinfections are likely to occur, we intend to analyse differences in periods, along with associated risk-factors, using Bayesian exponential survival regression models with non to weakly informative *a priori* distributions.(68)

For all other secondary study parameters, continuous variables will be summarized using means or medians and categorical variables using counts and percentages at each study visit. Changes over time will be described for HCV related risk behaviour, disinfection behaviour and sexual wellbeing. We will use statistical regression methods specific to the endpoint (logistic for binary outcomes, linear for continuous variables), corrected for repeated measurements within individuals (using mixed-effect methods) to investigate changes between lead-in and intervention periods and associated determinants. Outcomes will also be compared across the 3 arms.

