2.1.2. Secondary endpoints

- **Definition**

Secondary endpoints are as follows:

- Incidence rate of HCV reinfections during both the run-in (i.e., M0 and M6) and intervention period (i.e., M12, M18, M24), both self-reported and laboratory-confirmed, defined as the number of cases divided by the total person-years of follow-up at risk for reinfection
- Incidence rate of any STI during the run-in and intervention period, both self-reported and laboratory-confirmed, defined as the number of chlamydia, gonorrhoea, genital herpes and/or syphilis infections divided by the total person-years of follow-up
- Other HCV-related risk behaviour during run-in versus intervention period, more specifically:
 - Changes in the mean or median number of sex partners (depending on the distribution of the variable of interest)
 - Changes in the mean or median number of condomless anal sex acts with casual partners (depending on the distribution of the variable of interest)
 - Changes in the proportion of participants reporting any individual behaviours that are included in the HCV-MOSAIC risk score
 - Changes in mean or median sexual wellbeing score (depending on the distribution of the variable of interest)
- The proportion of participants achieving an HCV-MOSAIC risk score ≥ 2.0 at the end of follow-up compared between intervention arms (in both ITT and PP populations)

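### Protocol 9.2 plans to compare secondary outcomes across the three arms, but the SAP specifies only run-in versus intervention contrasts for behaviour items, wellbeing, STI and reinfection

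*SAP*

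**What the plan says.** Protocol 9.2 has two paragraphs. The first deals with reinfection and STI incidence. For reinfection, "we intend to analyse differences in periods, along with associated risk-factors, using Bayesian exponential survival regression models"; for STI it says only that rates will be calculated. The second paragraph begins "For all other secondary study parameters, continuous variables will be summarized using means or medians", describes mixed-effect models of change between lead-in and intervention, and ends with "Outcomes will also be compared across the 3 arms".

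SAP 2.2.2 covers the same outcomes by period:

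- Reinfection: "we intend to analyse the relative difference in incidence rates between periods using a Bayesian exponential survival regression model".
- STI: "The relative difference in incidence rates of STIs are compared between periods using a Poisson regression model".
- Behaviour and wellbeing: "The relative changes in each endpoint are compared between run-in and intervention periods".

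Arm enters only as a stratifier: "These models are run on both the overall study population and stratified by treatment arm". SAP 3.5.1 to 3.5.4 add no contrast between arms. The exception is the HCV-MOSAIC cut-off, which SAP 2.1.2 and 3.5.5 evaluate "at the end of follow-up compared between intervention arms (in both ITT and PP populations").

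**The concern.** A result stratified by arm is a before-after comparison repeated three times. It does not compare randomised groups. Protocol section 3 explains that there is no untreated arm, so each within-arm change combines the intervention effect with whatever else changed for all participants over 24 months: calendar trends, repeated questionnaires, ageing. The documents point to such influences themselves. SAP 3.3.3 records the influence of COVID-19 measures and mpox on sexual behaviour, and Protocol 1.3 reports that Dutch HCV incidence was already falling.

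An influence that acts equally on all arms cancels, on the model scale, when arms are compared. The between-arm contrast is therefore the comparison that randomisation protects. It also bears on the hypothesis in Protocol 5.3 that the combined intervention reduces risk behaviour most. For partner numbers, condomless acts, individual risk items and wellbeing, the SAP as written gives no estimate of whether one arm changed more than another. Readers would be left to compare three separate p-values.

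**Working it through.** **1. The texts side by side**

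| Outcome | Protocol 9.2 | SAP 2.2.2 and 3.5 |
|---|---|---|
| Behaviour items, wellbeing | Lead-in v intervention, and across arms (same paragraph) | Run-in v intervention, overall and by arm |
| Reinfection | Between periods; across arms only if the closing sentence covers all of 9.2 | Between periods, overall and by arm |
| STI | Rates calculated; across arms only on the same broad reading | Between periods, overall and by arm |
| HCV-MOSAIC ≥ 2.0 | Period-by-arm interaction (Protocol 9.1) | Between arms at end of follow-up |

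The SAP gives no reason for omitting the across-arm step.

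**2. The plan's own power figures (primary endpoint only)**

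- Within arm, 60% to 38%, n = 78, two-sided 0.05, periods treated as independent: the pooled SE is √(2 × 0.49 × 0.51/78) = 0.0800 and the unpooled SE is √((0.24 + 0.2356)/78) = 0.0781. Then (0.22 − 1.96 × 0.0800)/0.0781 = 0.81, so power is 79.1% against the stated 80%. The figure is reproduced.
- Between arms, Protocol 4.4 gives 80% power for a reduction of 0.43 against 10%. Read as absolute reductions from 60% with independent periods, the SE is √((0.24 + 0.25 + 0.24 + 0.1411)/78) = 0.1057. Then 0.33/0.1057 − 1.96 = 1.16, so power is 87.8%; 80% is reached at a reduction of about 0.40. The protocol figure came from simulation, so exact agreement is not expected. On either figure, only a large difference between arms is detectable for a binary outcome.

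Neither figure concerns the secondary outcomes.

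**3. What three within-arm tests show**

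Suppose all arms have the same true effect and each test has 80% power (assumption). The chance that the arms disagree on significance is 1 − 0.8³ − 0.2³ = 0.48. At 50% power it is 1 − 0.5³ − 0.5³ = 0.75. Differing p-values would therefore be common without any difference between arms.

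**4. A shared influence**

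Suppose an external change multiplies STI rates by 0.70 in every arm and no intervention has an effect (assumption). Each within-arm rate ratio is 0.70, and the ratio of any two is 0.70/0.70 = 1.0.

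**5. Precision of an arm-by-period contrast for a continuous outcome**

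Inputs: n = 78 per arm (SAP 1.4); within-person correlation r = 0.5 (assumption, no source in the documents); compound symmetry; no missing data. With a run-in and b intervention values per man,

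SE = SD × √[(2/78) × (1 − r) × (1/a + 1/b)].

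- a = 1, b = 1: √[(2/78) × 0.5 × 2] = 0.160 SD; 80% power at 2.80 × 0.160 = 0.45 SD.
- a = 2, b = 3: √[(2/78) × 0.5 × (1/2 + 1/3)] = 0.103 SD; 80% power at 2.80 × 0.103 = 0.29 SD.

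**6. Precision for a binary outcome**

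Comparing two arms at a single time point with 78 each, about 80% power needs an absolute difference of about 15 points from 20%, 18.5 from 30%, 20.5 from 40%, 22 from 50% or 22.5 from 60%. The starting rates are assumptions, because the documents give none for the secondary outcomes.

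**The case against.** The other side has four good arguments.

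- **Scope.** A reader might infer that the protocol promises an across-arm comparison for every secondary outcome. Its sentence closes the paragraph on the remaining parameters, after reinfection and STI have been dealt with separately. For those two the SAP's between-period plan matches the protocol's own paragraph on reinfection and does not contradict the one on STI. This stands: the inconsistency is clear only for behaviour items and wellbeing.
- **Nothing is irretrievable.** A reader might infer that the randomised comparison has been lost. The SAP does not withdraw the protocol sentence, results are produced by arm, and one between-arm analysis remains. The secondary models probably inherit the arm-by-time-point interaction of the primary model, although the SAP's reference to the same fixed-effect configuration could mean only the adjustment sets. This also stands: the contrast is unspecified, but the data allow it.
- **Design.** Protocol section 3 presents the trial as a pilot of change within each arm, and the primary objective is change against run-in. Between-arm contrasts here compare active arms only and are supplementary. That is true, but Protocol 9.2 planned them nonetheless.
- **Power and multiplicity.** Protocol 9.1 calls the interaction test possibly underpowered, and 9.2 expects few reinfections. Two partner and act counts, six items and wellbeing give 9 × 3 = 27 pairwise contrasts; adding STI and reinfection gives 11 × 3 = 33. This argues for cautious labelling. It does not justify dropping a planned comparison without comment.

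**Conclusion.** The point holds in limited form. The protocol commits to comparing behaviour items and sexual wellbeing across arms, and the SAP specifies no such comparison and gives no reason. For STI and reinfection the same addition is desirable on randomisation grounds, but calling it a broken commitment would need a reading the text does not compel. The contrast has been left unspecified and remains estimable.

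The consequence is one of interpretation. Without an untreated arm, the specified secondary results cannot separate an intervention effect from an influence shared by all men. The 0.70 versus 1.0 example illustrates this and does not forecast its size. It also assumes that the shared influence acts equally across arms.

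A reader might infer from section 5 of the working that precision is adequate. That does not follow: 0.160 and 0.103 SD rest on an assumed correlation of 0.5 and complete data, apply to continuous outcomes, and would worsen with loss after randomisation. Most of the listed outcomes are binary items or event rates, for which the detectable differences are large. For reinfection, even the randomised contrast needs care, because Arms II and III are offered four extra tests and detection may differ by arm.

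**What to change.** In SAP 2.2.2, 3.5.3 and 3.5.4:

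- Write the arm-by-period interaction explicitly into the models for behaviour items and wellbeing.
- Report three contrasts for each outcome (III v I, III v II, I v II) with 95% confidence intervals. This mirrors the period-by-arm term that Protocol 9.1 already sets out for the primary outcome.
- Label the results secondary or exploratory, state that no multiplicity adjustment is made, and make no claim of adequate power.

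Preferably do the same in 3.5.1 and 3.5.2: a ratio of rate ratios for STI, and the corresponding contrast with a credible interval from the Bayesian model for reinfection. Show the number of HCV RNA tests per arm beside the reinfection result.

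If the across-arm comparison is deliberately being dropped, record that as a departure from Protocol 9.2 and give the reason.

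The cost is SAP wording and extra table columns, with no new data. The downside is 27 to 33 additional estimates, many of them imprecise and all unadjusted, which show the relative effect of active arms and not the effect against no intervention.
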